#### **6.6.2 Emergency breaking of assigned treatment code**

Not applicable

## 6.7 Preparation and dispensation

### **MBG453 (sabatolimab)**

MBG453 (sabatolimab) (800 mg) will be administered IV. Further instructions for the preparation and dispensation of MBG453 (sabatolimab) are described in the Pharmacy Manual.

All dosages for MBG453 (sabatolimab) prescribed to the participant and all dose changes during the study must be recorded on the Dosage Administration Record eCRF.

### **Decitabine (IV and INQOVI (oral decitabine))**

For details on preparation refer to the US package insert instructions and/or IV decitabine or INQOVI (oral decitabine) package insert, if the drug is commercially available. All dosages for decitabine or INQOVI (oral decitabine) prescribed to the participant and all dose changes during the study must be recorded on the Dosage Administration Record eCRF.

### **Azacitidine**

For details on preparation refer to the US package insert instructions and/or azacitidine package insert, if the drug is commercially available. All dosages for azacitidine prescribed to the participant and all dose changes during the study must be recorded on the Dosage Administration Record eCRF.

### **Public Health emergency**

As per section 4.6, during a Public Health emergency as declared by Local or Regional authorities i.e. pandemic, epidemic or natural disaster, that limits or prevents on-site study visits, delivery of IMP directly to a participant's home may be permitted (if allowed by Local or Regional Health Authorities and Ethics Committees as appropriate) in the event the Investigator has decided that an on-site visit by the participant is no longer appropriate or possible, and that it is in the interest of the participant's health to administer the study treatment even without performing an on-site visit. The dispatch of IMP from the site to the participant's home remains under the accountability of the Investigator. Each shipment/provisioning will be for a maximum of X-months supply. In this case, regular phone calls or virtual contacts (every Y weeks or more frequently if needed) will occur between the site and the participant for instructional purposes, safety monitoring, drug accountability, investigation of any adverse events, ensuring participants continue to benefit from treatment and discussion of the participant's health status until the participants can resume visits at the study site.

#### **6.7.1 Handling of study treatment and additional treatment**

##### **6.7.1.1 Handling of study treatment**

Study treatment must be received by a designated person at the study site, handled and stored safely and properly and kept in a secured location to which only the investigator and designated site personnel have access. Upon receipt, all study treatments must be stored according to the instructions specified on the labels and in the Investigator's Brochure. Clinical supplies are to

be dispensed only in accordance with the protocol. Technical complaints are to be reported to the respective Novartis CO Quality Assurance.

Medication labels will be in the local language and comply with the legal requirements of each country. They will include storage conditions for the study treatment but no information about the participant except for the medication number.

The investigator must maintain an accurate record of the shipment and dispensing of study treatment in a drug accountability log. Monitoring of drug accountability will be performed by monitors during site visits or remotely and at the completion of the trial.

At the conclusion of the study, and as appropriate during the course of the study, the investigator will return all unused study treatment, packaging, drug labels, and a copy of the completed drug accountability log to the field monitor or to the Novartis address provided in the investigator folder at each site.

#### **6.7.1.2 Handling of additional treatment**

Not applicable

#### **6.7.2 Instruction for prescribing and taking study treatment**

Refer to [Section 6.1](#).

### **7 Informed consent procedures**

Eligible participants may only be included in the study after providing (witnessed, where required by law or regulation), Institutional Review Board (IRB) / Institutional Ethics Committee (IEC) approved informed consent.

If applicable, in cases where the participant's representative(s) gives consent (if allowed according to local requirements), the participant must be informed about the study to the extent possible given his/her understanding. If the participant is capable of doing so, he/she must indicate agreement by personally signing and dating the written informed consent document.

Informed consent must be obtained before conducting any study-specific procedures (e.g. all of the procedures described in the protocol). The process of obtaining informed consent must be documented in the participant source documents.

The date when a participant's Informed Consent was actually obtained will be captured in their CRFs.

Novartis will provide to investigators in a separate document a proposed informed consent form that complies with the ICH GCP guidelines and regulatory requirements and is considered appropriate for this study. Any changes to the proposed consent form suggested by the investigator must be agreed by Novartis before submission to the IRB/IEC.

Information about common side effects already known about the investigational drug can be found in the Investigator's Brochure (IB). This information will be included in the participant informed consent and should be discussed with the participant during the study as needed. Any new information regarding the safety profile of the investigational drug that is identified between IB updates will be communicated as appropriate, for example, via an investigator

notification or an aggregate safety finding. New information might require an update to the informed consent and then must be discussed with the participant.

The study includes the option for the subjects to continue MBG453 alone. The study also includes the option for the subjects to continue treatment with MBG453 and azacitidine/decitabine/INQOVI (oral decitabine), azacitidine/decitabine/INQOVI (oral decitabine) alone, MBG453 alone beyond progression in selected subjects without acute leukemia (see [Section 6.1.4.1](#)).

In both options (continuation of MBG453 alone, or continuation of treatment beyond progression), this will require informed consent before treatment continuation if the subject agrees to participate. It is required as part of this protocol that the investigator presents these options to the subjects, as permitted by local governing regulations. The process for obtaining consent should be the same as described above for the main informed consent.

Women of child-bearing potential must be informed that taking the study treatment may involve unknown risks to the fetus if pregnancy were to occur during the study and agree that in order to participate in the study they must adhere to the contraception requirements for the duration of the study and 150 days after the last dose of MBG453 (sabatolimab).

Male participants, including vasectomized men, in the study, must agree not to father a child and to use a condom during intercourse, to prevent delivery of the drug via seminal fluid during the study, and for the period of 3 months after the last dose of azacitidine or decitabine or INQOVI (oral decitabine).

Prior to starting treatment, male participants are advised to seek consultation on sperm storage and female participants of child-bearing potential should seek consultation regarding oocyte cryopreservation.

If there is any question that the participant will not reliably comply, they should not be entered in the study.

A copy of the approved version of all consent forms must be provided to Novartis after IRB/IEC approval.

As per section 4.6, during a Public Health emergency as declared by Local or Regional authorities i.e. pandemic, epidemic or natural disaster, that may challenge the ability to obtain a standard written informed consent due to limits that prevent an on-site visit, Investigator may conduct the informed consent discussion remotely (e.g. telephone, videoconference) if allowable by a local Heath Authority.

Guidance issued by local regulatory bodies on this aspect prevail and must be implemented and appropriately documented (e.g. the presence of an impartial witness, sign/dating separate ICFs by trial participant and person obtaining informed consent, etc.).

## 8 Visit schedule and assessments

Assessment schedules ([Table 8-1](#)) lists all of the assessments and indicates with an “X”, the visits when they are performed. All data obtained from these assessments must be supported in the participant’s source documentation.

No eCRF will be used as a source document.

Each treatment cycle is 28 days. Screening evaluations should be performed within  $\leq$  28 days of Cycle 1 Day 1 (except for the pregnancy test which has to be performed within 72 hours before the first dose). Bone marrow aspirate (BMA) or biopsy performed prior to signing informed consent but within 28 days from the informed consent, may be used. [REDACTED]

[REDACTED] Instead, a viable cryopreserved BMA sample collected prior to informed consent signature (but within 28 days from the informed consent) should be provided, if available.

If the hematology and chemistry laboratory tests are performed within 7 days before enrollment, it is not required to perform them again on C1D1.

During the course of the study visits, test and/or procedures should occur on schedule whenever possible. During the core phase and extension phase, a visit window of  $+\text{-} 7$  days is allowed. During the post-treatment follow up phase a visit window of  $+\text{-}14$  days is allowed.

In case the infusion of MBG453 (sabatolimab), azacitidine or decitabine cannot be administered at the scheduled visit, it has to be administered as soon as possible. Every effort should be made on C1D1 for the drug to be administered on the same day as enrollment. A visit window of  $+7$  days is allowed for treatment administration for reason other than toxicities. [REDACTED]

Participants who discontinue the study treatment for any reason should be scheduled for an end of treatment (EOT) visit within 7 days from the date that the participant discontinued from treatment, at which time all of the assessments listed for the EOT visit will be performed (if bone marrow aspirate or biopsy was performed within 14 days from the EOT visit, the assessment does not have to be repeated).

All participants receiving the study treatment must have safety evaluations for 30 days after the last dose of decitabine or INQOVI (oral decitabine) or azacitidine, or 150 days after the last dose of MBG453 (sabatolimab), whichever occurs later. After the safety follow-up on site visit on Day 30, participants will be followed via telephone call for the Day 90 and Day 150 (or onsite visit if patient happens to be visiting the site).

For post-treatment follow-up and survival information, please refer to [Section 9.1.6](#).

As per section 4.6, during a Public Health emergency as declared by Local or Regional authorities i.e. pandemic, epidemic or natural disaster that limits or prevents on-site study visits, alternative methods of providing continuing care may be implemented by the investigator as the situation dictates. If allowed by local Health Authority and depending on operational capabilities, phone calls, virtual contacts (e.g. tele consult) or visits by site staff/ home nursing staff to the participant’s home, can replace on-site study visits, for the duration of the disruption until it is safe for the participant to visit the site again.

**Table 8-1 Assessment Schedule**

Period	Scr	Core														EOT 7		
		Cycle 1 (28d)		Cycle 2 (28d)		Cycle 3 (28d)		Cycle 4 (28d)		Cycle 5 (28d)		Cycle 6 (28d)		Cycle 7 (28d)		Cycle 8 (and beyond until Cycle 13) (28d) 		
Cycle		1	2	3	4	5	6	7	8	9	10	11	12	13	14	15 (17, 19, 21 +)	16 (18, 20, 22)	EOT 7
Visit Name	Scr eeni	1	2	3	4	5	6	7	8	9	10	11	12	13	14	15 (17, 19, 21 +)	16 (18, 20, 22)	EOT 7
Days	-28 to -1	D1	D8 1	D1	D8 1	D1	D8 1	D1	D8 1	D1	D8 1	D1	D8 1	D1	D8 1	D1	D8 1	-
BSA (use height from screening)		X		X		X		X		X		X		X		X		
Body Weight	X	X		X		X		X		X		X		X		X		X
ECOG PS	X	X		X		X		X		X		X		X		X		X
12-Lead ECG (triplicates)	S	If clinically indicated														S		
Hematology	X 2	X	X	X	X	X	X	X	X	X	X	X	X	X	X	X		X
Chemistry	X 2	X		X		X		X		X		X		X		On cycle 9, 11, and 13		X
Coagulation	X	X		X		X		X		X		X		X		On cycle 9, 11, and 13		X
Thyroid function	X			X						X						On cycle 8 and 11		X

Period	Scree	Core														EOT 7		
		Cycle 1 (28d)		Cycle 2 (28d)		Cycle 3 (28d)		Cycle 4 (28d)		Cycle 5 (28d)		Cycle 6 (28d)		Cycle 7 (28d)		Cycle 8 (and beyond until Cycle 13) (28d) 		
Cycle		1	2	3	4	5	6	7	8	9	10	11	12	13	14	15 (17, 19, 21)	16 (18, 20, 22 +)	EOT 7
Visit Name	Scree ning	1	2	3	4	5	6	7	8	9	10	11	12	13	14	15 (17, 19, 21)	16 (18, 20, 22 +)	EOT 7
Days	-28 to -1	D1	D8 1	D1	D8 1	D1	D8 1	D1	D8 1	D1	D8 1	D1	D8 1	D1	D8 1	D1	D8 1	-
Virology hepatitis B and C	S	If clinically indicated																
HIV serology (only if required per local regulation)	S																	
Serum Pregnancy Test (only women with child-bearing potential)	S	S															S	
Urine Pregnancy Test OR Serum Pregnancy Test (only women with child-bearing potential)			S		S		S		S		S		S		S			
Urinalysis dipstick and sediment	S																	
Efficacy - Bone marrow aspirate and/or biopsy 	X 3							X								On cycle 10 and 13		X

Period	Screening	Core																EOT 7
Cycle		Cycle 1 (28d)		Cycle 2 (28d)		Cycle 3 (28d)		Cycle 4 (28d)		Cycle 5 (28d)		Cycle 6 (28d)		Cycle 7 (28d)		Cycle 8 (and beyond until Cycle 13) (28d) 7		
Visit Name	Screening	1	2	3	4	5	6	7	8	9	10	11	12	13	14	15 (17, 19, 21)	16 (18, 20, 22 +)	EOT 7
Days	-28 to -1	D1	D8 1	D1	D8 -1	D1	D8 -1	D1	D8 1	D1	D8 1	D1	D8 1	D1	D8 -1	D1	D8 1	-
Efficacy - Peripheral blood collections 	X							X						X		On cycle 10, 13 and if clinically indicated		X
Cytogenetics	X																	
Response assessment														X		On cycle 13 and if clinically indicated		X

Period	Extension												
	Cycle 1 (28d)	Cycle 2 (28d)	Cycle 3 (28d)	Cycle 4 (28d)	Cycle 5 (28d)	Cycle 6 (28d)	Cycle 7 (28d)	Cycle 8 (28d)	Cycle 9 (28d)	Cycle 10 (28d)	Cycle 11 (28d)	Cycle 12 (28d)	Cycle 13 (28d)
Visit Name	Ext 1	Ext 2	Ext 3	Ext 4	Ext 5	Ext 6	Ext 7	Ext 8	Ext 9	Ext 10	Ext 11	Ext 12	Ext 13
Decitabine infusion	If chosen and continuing treatment: on Days 1-5 of each cycle												
Oral decitabine/cedazuridine	If chosen and continuing treatment: on Days 1-5 of each cycle												
Infusion Drug Dispensation MBG453 (sabatolimab) 	If continuing treatment : on D8 of every cycle												
Adverse Events a	Continuous												
Concomitant medications and medical procedures (including blood transfusions requirement)	Continuous												
Antineoplastic therapies, HSCT and transfusions since discontinuation of study treatments b	[REDACTED]												
Disposition													X
Survival Follow up	X						X						X

Period	Post-treatment Safety FU	
Cycle		
Visit Name	D30	D150 and beyond
Days	-	-
Serum Pregnancy Test (only women with child-bearing potential)		S (D150 only)
Urine Pregnancy Test OR Serum Pregnancy Test (only women with child-bearing potential)	S (D30, D60, D90, D120 after the last dose of MBG453 (sabatolimab))	
Adverse Events 	Continuous until D30 or D150	
Concomitant medications and medical procedures (including blood transfusions requirement)	Continuous	
Antineoplastic therapies, HSCT and transfusions since discontinuation of study treatment	Continuous	
Survival Follow up	Every 6 cycles	

X Assessment to be recorded in the clinical database or received electronically from a vendor

S Assessment to be recorded in the source documentation only

1. For hospital administered HMAs (IV and SC – decitabine 20mg/m^2 D1-D5; or azacitidine 75mg/m^2 D1-D7 or D1 to D5 + D8 & D9), for flexibility of administration of the investigational therapy (sabatolimab) can be administered on any day from D5-D8 based on investigator/patient decision. Currently no data is available on administration of sabatolimab on day 5, 6 or 7. Further data will be collected and evaluated through this study. Based on prior trials change of day of administration and frequency [every two weeks vs. every four weeks] within the cycle of MBG53 may not have additional [REDACTED] safety concerns.
2. If the hematology and chemistry laboratory tests are performed within 7 days before enrollment, it is not required to perform them again on C1D1.
3. If bone marrow results are available within 28 days prior to informed consent, the procedure does not have to be repeated at screening, the results can be used for diagnosis and baseline. Bone marrow aspirate (BMA) or biopsy performed prior to signing informed consent but within 28 days from the informed consent, may be used. [REDACTED]

[REDACTED] Instead, a viable cryopreserved BMA sample collected prior to informed consent signature (but within 28 days from the informed consent) should be provided, if available.

4. [REDACTED]
5. Bone marrow aspirate and/or biopsy and peripheral blood samples for efficacy assessments should be performed at screening and pre-dose during treatment period (C4D1, C7D1, C10D1, C13D1), and when clinically indicated at any time during the study
6. Exploratory analysis at Garcia-Manero et al EHA 2020 revealed that patient treated with anti-TIM3 antibody MBG453 (sabatolimab) in combination with HMA for MDS and AML can successfully proceed to allogenic stem cell transplant. To date there are limited toxicity for GVHD. Further data is required.
7. Patient can enter extension phase per investigator decision.
8. To be collected only for patients continuing MBG453 (sabatolimab) treatment. See section 10.1.1.
9. Post treatment safety follow-up monitoring for adverse events (AEs) for 30 days following the last dose of azacitidine or decitabine or INQOVI (oral decitabine), or 150 days following the last dose of MBG453 (sabatolimab), whichever is later. See section 10.1.1.

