Post treatment follow up is for safety collection and is up to 150 days post core phase or extension phase discontinuation (see [Figure 3-1](#)). Survival data will be collected until end of study inclusive of the extension and post treatment follow up duration.

Treatment options and dosing information are provided in [Section 6.1](#). The planned duration of a cycle is 28 days.

Participants who become eligible for hematopoietic stem cell transplant (HSCT) at any time during the course of the study will be discontinued from investigational study treatment (MBG453 (sabatolimab)).

All participants must be followed for adverse events (AEs) after the last dose of MBG453 (sabatolimab) as indicated in [Section 10.1](#). All women of child-bearing potential must be followed for pregnancy safety evaluations as per [Table 8-1](#) and after last dose of MBG453 (sabatolimab) as indicated in [Section 10.1.4](#).

At the end of the study, every effort will be made, in alignment with local regulations, to continue provision of MBG453 (sabatolimab) outside this study through an alternative setting to participants who are receiving treatment with MBG453 (sabatolimab) and in the opinion of the investigator are still deriving clinical benefit. Options for continued treatment with MBG453 (sabatolimab) may include access to commercially available drug, or managed access program, or a roll-over study.

[figure not shown]
There are four separate periods of this study:

1. Screening period (signing of written informed consent through Day of enrollment);
2. Core phase for up to 12 months
3. Extension phase for efficacy and/or survival status (up to 12 months after core phase)
4. post treatment safety follow-up monitoring for adverse events (AEs) for 30 days following the last dose of azacitidine or decitabine or INQOVI (oral decitabine), or 150 days following the last dose of MBG453 (sabatolimab), whichever is later.

[figure not shown]
Approximately 39 patients who are evaluable for primary endpoints will be assessed.

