19. Sexually active males unwilling to use a condom during intercourse while taking azacitidine or decitabine or INQOVI (oral decitabine) and for 3 months after stopping these drugs. A condom is required for all sexually active male participants to prevent them from fathering a child AND to prevent delivery of study treatment via seminal fluid to their partner. In addition, male participants must not donate sperm for the time period specified above, and their female partners will be instructed to use highly effective contraception.
20. Participant is pregnant or breastfeeding.
21. Women of child-bearing potential, defined as all women physiologically capable of becoming pregnant, unless they are using highly effective methods of contraception during study treatment and for 3 months after the last dose of azacitidine or decitabine or INQOVI (oral decitabine) (or as per their respective local labels, whichever is longer) and 150 days after the last dose of MBG453 (sabatolimab). Highly effective contraception methods include:
  - Total abstinence (when this is in line with the preferred and usual lifestyle of the participant). Periodic abstinence (e.g. calendar, ovulation, symptothermal, post-ovulation methods) and withdrawal are not acceptable methods of contraception
  - Female sterilization (have had surgical bilateral oophorectomy with or without hysterectomy), total hysterectomy or bilateral tubal ligation at least 6 weeks before taking study treatment. In case of oophorectomy alone, only when the reproductive status of the woman has been confirmed by follow up hormone level assessment
  - Male sterilization (at least 6 months prior to screening). For female participants on the study the vasectomized male partner should be the sole partner for that participant.
  - Use of oral (estrogen and progesterone), injected or implanted combined hormonal methods of contraception or placement of an intrauterine device (IUD) or intrauterine

system (IUS) or other forms of hormonal contraception that have comparable efficacy (failure rate <1%), for example hormone vaginal ring or transdermal hormone contraception

In case of use of oral contraception, women should have been stable on the same pill for a minimum of 3 months before taking study treatment.

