**Table 8-5 Local clinical laboratory parameters collection plan**

Test Category	Test Name
Hematology	Hematocrit, Hemoglobin, MCH, MCHC, MCV, Platelets, Red blood cells, White blood cells, RBC Morphology, Differential (Basophils, Eosinophils, Lymphocytes, Monocytes, Neutrophils, Bands), Blasts, Other (absolute value preferred, %s are acceptable)
Chemistry	Albumin, Alkaline phosphatase, ALT, AST, Gamma-glutamyl-transferase (GGT), Lactate dehydrogenase (LDH), Calcium, Magnesium, Phosphorus, Sodium, Potassium, Creatinine, Creatine kinase, Direct Bilirubin, Indirect Bilirubin, Total Bilirubin, Total Cholesterol, Total Protein, Blood Urea Nitrogen (BUN) or Urea, Uric Acid, Amylase, Lipase, Glucose (fasting), Troponin T
Virology*	HBsAg, HBcAb, HBV DNA (in participants positive for HBcAb), HCV RNA (PCR) HIV (Only if required by local regulation)
Coagulation	International normalized ratio (INR), Activated partial thromboplastin time (aPTT)
Cytokines***	IFN- $\gamma$ , IL-6, IL-1, TNF- $\alpha$
Urinalysis dipstick and sediment*	Dipstick examination includes specific gravity, pH, glucose, protein, blood, bilirubin, ketones and WBC as clinically indicated
Pregnancy Test*	Serum / Urine pregnancy test (refer to 'Pregnancy and assessments of fertility' section)

\*Virology, urinalysis and pregnancy test will only be reported in the source documentation.

\*\*Preferred method is erythrocyte folate but in case is not available then serum should be performed. However, every effort should be made to perform both test.

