### **8.4.3 Pregnancy and assessments of fertility**

#### **Female patients**

All pre-menopausal women who are not surgically sterile will have pregnancy testing. Additional pregnancy testing might be performed if requested by local requirements.

At screening, a serum pregnancy test (serum  $\beta$ -HCG) must be performed within 72 hours before the first dose of study treatment.

During the study, a urine/serum pregnancy test should be done locally at Day 1 of each cycle (except if for Cycle 1 a pregnancy test was performed within 72 hours of the first dose) and at EOT visit. Additionally, during the post treatment safety follow up, women of child bearing potential will be tested monthly with urine or serum pregnancy tests up to Day 90 after the last dose of azacitidine or decitabine or INQOVI (oral decitabine). They will also be tested monthly with urine or serum pregnancy tests up to Day 150 after the last dose of MBG453 (sabatolimab), and a serum pregnancy test should be performed on Day 150 after the last dose of MBG453 (sabatolimab). If the participant is not coming to the clinic during the safety follow-up period, the test can be performed at home or at a local doctor's office, and the results will be communicated to the site staff.

A positive urine pregnancy needs to be confirmed with a serum test. Confirmed positive pregnancy test requires immediate discontinuation of study treatment and discontinuation from study see [Section 10.1.4](#) for pregnancy reporting.

The pregnancy tests will be recorded only in the source documentation, not in the CRF.

Women of childbearing potential should employ the use of highly effective contraception during study treatment, for 3 months after the last dose of azacitidine or decitabine or INQOVI (oral decitabine) (or as per their respective local labels, whichever is longer) and 150 days after the last dose of MBG453 (sabatolimab). Highly effective contraception methods are defined in [Section 5.2](#).

Medical documentation of oophorectomy, hysterectomy, or tubal ligation must be retained as source documents. Subsequent hormone level assessment to confirm the woman is not of child-bearing potential must also be available as source documentation in the following cases:

1. Surgical bilateral oophorectomy without a hysterectomy
2. Reported 12 months of natural (spontaneous) amenorrhea with an appropriate clinical profile.

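### Table 8-1 times the monthly post-treatment pregnancy tests from the last sabatolimab dose only, contradicting section 8.4.3, which also requires tests to Day 90 after the last HMA dose

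*Protocol*

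**What the plan says.** Protocol Table 8-1, post-treatment safety follow-up, gives the timing of the urine or serum pregnancy test as "S (D30, D60, D90, D120 after the last dose of MBG453 (sabatolimab"). The serum-test row has a Day 150 entry that names no drug. Both rows are legible, and neither mentions an HMA.

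Protocol section 8.4.3 (Female patients) says that women of child-bearing potential are to be "tested monthly with urine or serum pregnancy tests up to Day 90 after the last dose of azacitidine or decitabine or INQOVI". It adds a second requirement: monthly tests to Day 150 after the last sabatolimab dose, with a serum test on that day. Exclusion criterion 21 in section 5.2 asks for contraception "for 3 months after the last dose of azacitidine or decitabine or INQOVI (oral decitabine"), or longer where the local label says so, as well as for 150 days after sabatolimab. Section 8.4.3 restates both contraception periods.

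The protocol is divided on which text a site should follow. Section 8 says that Table 8-1 "lists all of the assessments". Section 3 says "All women of child-bearing potential must be followed for pregnancy safety evaluations as per" Table 8-1, and then cites section 10.1.4, which covers pregnancy reporting and holds no test schedule. Table 8-5, by contrast, has the entry "Serum / Urine pregnancy test (refer to 'Pregnancy and assessments of fertility' section"), which leads to 8.4.3.

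During treatment, 8.4.3 states that "a urine/serum pregnancy test should be done locally at Day 1 of each cycle", and again at the end-of-treatment (EOT) visit. Section 8 schedules an "end of treatment (EOT) visit within 7 days from the date that the participant discontinued from treatment".

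**The concern.** The protocol allows a woman to stop sabatolimab and continue an HMA alone (sections 6.1.4, 6.5 and 9.1.5). The two clocks in 8.4.3 then separate, and the table keeps only the one that started earlier. A site that builds its follow-up calendar from section 3 and Table 8-1 never meets the HMA clock and may stop testing while 8.4.3 still requires it.

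The risk is a pregnancy that goes undetected in the months after an HMA. The general safety follow-up is not a reliable backstop. It ends at the later of 30 days after the HMA and 150 days after sabatolimab, so once the last HMA dose is 120 or more days (150 - 30) after the last sabatolimab dose it ends at HMA Day 30, 60 days before testing under 8.4.3 should end. Pregnancy tests are recorded in source documents only, so a missed test would not show in the study database.

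**Working it through.** The plan states no figure to reproduce. The check is day arithmetic on nominal days.

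**Inputs.** A cycle is 28 days (section 3). Sabatolimab is given on Day 8, or on any day from Day 5 to Day 8 with IV or SC HMAs (Table 6-1). The last HMA day in a cycle is Day 5 for decitabine and Day 7 or Day 9 for azacitidine (Table 6-2). Table tests fall at sabatolimab Days 30, 60, 90, 120 and 150. I assume that the Day 150 entry means sabatolimab Day 150, as in 8.4.3, and that no cycle is delayed.

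**Formulas.** Let x be the days from the last sabatolimab dose to the last HMA dose, and n the number of HMA-only cycles.

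- x = 28n + (last HMA day - sabatolimab day). The bracket runs from 5 - 8 = -3 to 9 - 5 = +4.
- HMA Day 90 falls on sabatolimab day x + 90.
- A table test at sabatolimab Day k falls on HMA Day k - x.
- The last table test reaches HMA Day 90 if 150 - x is at least 90, so a shortfall starts when x > 60. Its size is x - 60 as long as a table test still falls after the last HMA dose.

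| n | x (days) | HMA Day 90 on sabatolimab day | Table tests in the 90-day window (HMA Day) | Shortfall before HMA Day 90 |
|---|---|---|---|---|
| 0 | -3 to 4 | 87-94 | covered | none |
| 1 | 25-32 | 115-122 | covered | none |
| 2 | 53-60 | 143-150 | covered; last test at 90-97 | none |
| 3 | 81-88 | 171-178 | 2-9, 32-39, 62-69 | 21-28 days |
| 4 | 109-116 | 199-206 | 4-11, 34-41 | 49-56 days |
| 5 | 137-144 | 227-234 | 6-13 | one table test, plus EOT |
| 6 | 165-172 | 255-262 | none | EOT only |

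Monthly testing to Day 90 under 8.4.3 would give about three tests (Days 30, 60 and 90).

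**EOT test.** I give no day count for n = 5 or more, because the EOT visit is timed from treatment discontinuation and not from the last HMA dose. If discontinuation is decided at the end of the 28-day cycle, that is 28 - 9 = 19 to 28 - 5 = 23 days after the last HMA dose. With up to 7 more days for the visit, the EOT test falls on about HMA Day 19-30. On that assumption, 60-71 days (90 - 30 to 90 - 19) remain before HMA Day 90. For n = 3 and 4 the last table test is later than this, so those two shortfalls stand.

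**Visit window.** Section 8 allows plus or minus 14 days in post-treatment follow-up. The 3-cycle figure is the one most sensitive to this.

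**The case against.** The strongest reply is that the correct rule is already in force. Section 8.4.3 is the dedicated section on pregnancy testing, Table 8-5 points to it, and the proposed change adds no test to it. Harm requires a site to follow one table cell and overlook that section. This stands as a limit on the size of the problem. It does not remove the contradiction, because section 3 directs pregnancy follow-up to the table and to 10.1.4, and neither contains the HMA clock.

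A reader might infer more from the documents in three ways, none of which they support.

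- **That women on HMA alone go untested during treatment.** They do not. Section 6.1.4 keeps them on the treatment-phase assessments, with a test on Day 1 of each cycle and at EOT.
- **That after many HMA-only cycles the whole 90 days pass without a test.** This gives the EOT visit no credit, although it can fall about three weeks or more after the last HMA dose.
- **That women are given too short a contraception period at consent.** In section 7 the sentence for men names the 3 months after an HMA. The sentence for women names only the study duration and 150 days after sabatolimab, and section 13.3 names only the study duration. No shortfall follows. Sections 3 and 6.1.4 run follow-up to 150 days after leaving the core or extension phase, and section 9.1.6 follows survival to the end of study, so the study duration may already cover the 3 months. Section 4.5 ties women to the exclusion criteria, and the consent form is a separate document that was not reviewed.

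It is also fair to say that the remedy may come too late for this trial. Recruitment stopped on 30-Sep-2022, the SAP refers to termination of the sabatolimab programme, and its latest addendum (07-Feb-2025) is logged as after database lock.

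**Conclusion.** The contradiction between Table 8-1 and section 8.4.3 is real, and the table is wrong as written. It has an effect only for a woman of child-bearing potential whose last HMA dose is more than 60 days after her last sabatolimab dose. If both drugs stop together, or after one or two HMA-only cycles, the table already reaches HMA Day 90. Beyond that, the shortfalls in the table above apply to a site that schedules from Table 8-1 alone. They rest on undelayed 28-day cycles, nominal visit days and the Day 150 entry being counted from sabatolimab.

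The affected group is small and may be empty: 39 patients were enrolled, section 1.1 puts the median age at MDS diagnosis at about 70, and the documents do not give the number of women of child-bearing potential. This is a patient-safety inconsistency of low frequency, and it bears on no endpoint or analysis. The wording in sections 7 and 13.3 is a matter of harmonisation only.

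**What to change.** Change the post-treatment pregnancy rows of Table 8-1 to monthly urine or serum tests until the later of Day 90 after the last HMA dose and Day 150 after the last sabatolimab dose, with the serum test at sabatolimab Day 150. Add 8.4.3 to the pregnancy cross-reference in section 3. As minor harmonisation, have the sentences for women in sections 7 and 13.3 refer to the periods in exclusion criterion 21, and check that the consent form agrees.

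The cost is a wording amendment (two table rows, two sentences and one cross-reference) with sponsor and IRB/IEC approval under section 14.1, plus a consent-form revision only if the check finds a mismatch. If follow-up is already complete, the remaining steps are to check source records for any woman in the affected group and to correct the wording before the template is reused.
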